9.2.1 Adverse Events of Interest

Each AE of interest is defined in Appendix 4. Numbers and proportions of subjects with the following AEs of interest will be summarized by SOC and PT for each treatment group and for the overall brexpiprazole group.

- Extrapyramidal AEs
- Accident- and injury-related AEs
- Cerebrovascular AEs
- Cardiovascular AEs
- Glucose metabolism-related AEs
- Lipid metabolism-related AEs
- Body weight-related AEs
- Blood disorder-related AEs
- Hypersensitive symptom-related AEs
- Neuroleptic malignant syndrome-related AEs
- Orthostatic disorder-related AEs
- Prolactin increase-related AEs
- QT interval prolongation-related AEs
- Rhabdomyolysis
- Seizure-related AEs
- Oversedation-related AEs
- Suicide/suicide attempt-related AEs
- Venous thrombosis
- Pneumonia-related AEs

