Activated partial thromboplastin time abnormal

Activated partial thromboplastin time normal

Activated partial thromboplastin time prolonged

Activated partial thromboplastin time ratio

Activated partial thromboplastin time ratio abnormal

Activated partial thromboplastin time ratio decreased

Activated partial thromboplastin time ratio fluctuation

Activated partial thromboplastin time ratio increased

Activated partial thromboplastin time ratio normal

Activated partial thromboplastin time shortened

Activated protein C resistance

HAEMATOPOIETIC/LEUKOPENIA

Activated protein C resistance test

Activated protein C resistance test positive

Acute bilineal leukaemia

Acute biphenotypic leukaemia

Acute chest syndrome

Acute erythroid leukaemia

Acute febrile neutrophilic dermatosis

Acute haemolytic transfusion reaction

Acute haemorrhagic oedema of infancy

Acute leukaemia

Acute leukaemia in remission

Acute lymphocytic leukaemia

Acute lymphocytic leukaemia (in remission)

Acute lymphocytic leukaemia recurrent

Acute lymphocytic leukaemia refractory

Acute megakaryocytic leukaemia

Acute megakaryocytic leukaemia (in remission)

Acute monocytic leukaemia

Acute monocytic leukaemia (in remission)

Acute myeloid leukaemia

Acute myeloid leukaemia (in remission)

Acute myeloid leukaemia recurrent

Acute myeloid leukaemia refractory

Acute myelomonocytic leukaemia

Acute promyelocytic leukaemia

Acute undifferentiated leukaemia

Adenoiditis

Administration site lymphadenopathy

Adult T-cell lymphoma/leukaemia

Adult T-cell lymphoma/leukaemia recurrent

Adult T-cell lymphoma/leukaemia refractory

Adult T-cell lymphoma/leukaemia stage I

Adult T-cell lymphoma/leukaemia stage II

Adult T-cell lymphoma/leukaemia stage III

Adult T-cell lymphoma/leukaemia stage IV

Agranulocytosis

Agranulocytosis

Aleukaemic leukaemia

Allergic bronchopulmonary mycosis

Allergic eosinophilia

Allergic lymphangitis

Alloimmunisation

Alpha-thalassaemia-intellectual deficit syndrome

Amegakaryocytic thrombocytopenia

Anaemia

Anaemia Heinz body

Anaemia folate deficiency

Anaemia macrocytic

Anaemia megaloblastic

Anaemia neonatal

Anaemia of chronic disease

Anaemia of malignant disease

Anaemia of pregnancy

Anaemia postoperative

Anaemia splenic

Anaemia vitamin B12 deficiency

Anaemia vitamin B6 deficiency

Anaemic hypoxia

Anaemic retinopathy

Anaphylactoid syndrome of pregnancy

Anaplastic large cell lymphoma T- and null-cell types

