Indeterminable ABO blood type

Infantile genetic agranulocytosis

Infantile scurvy

Infected lymphocele

Infectious mononucleosis

Infusion site lymphadenopathy

Injection site lymphadenopathy

International normalised ratio

International normalised ratio abnormal

International normalised ratio decreased

International normalised ratio fluctuation

International normalised ratio increased

International normalised ratio normal

Intestinal T-cell lymphoma recurrent Intestinal T-cell lymphoma refractory

Intestinal T-cell lymphoma stage I

Intestinal T-cell lymphoma stage II

Intestinal T-cell lymphoma stage III

Intestinal T-cell lymphoma stage IV

Intravascular haemolysis

Iron deficiency anaemia

Isoimmune haemolytic disease

Jaundice

Jaundice acholuric

Jaundice neonatal

Jessner's lymphocytic infiltration

Juvenile chronic myelomonocytic leukaemia

Kell blood group positive

Lactescent serum

Langerhans cell sarcoma

Langerhans' cell histiocytosis

Large granular lymphocytosis

Leptomeningeal myelomatosis

Leukaemia

Leukaemia basophilic

Leukaemia cutis

Leukaemia granulocytic

Leukaemia in remission

Leukaemia monocytic

Leukaemia recurrent Leukaemic cardiac infiltration

Leukaemic infiltration

Leukaemic infiltration extramedullary

Leukaemic infiltration gingiva

Leukaemic infiltration hepatic

Leukaemic infiltration ovary

Leukaemic infiltration pulmonary

Leukaemic infiltration renal

Leukaemic lymphoma

Leukaemic retinopathy

Leukaemoid reaction

Leukocyte adhesion deficiency type I

Leukocyte vacuolisation

Leukocytosis

Leukoerythroblastic anaemia

Leukoerythroblastosis

Leukopenia

Leukopenia

Leukopenia neonatal

Leukopenia neonatal

Leukostasis syndrome

Light chain disease

Lineage switch leukaemia

Loeffler's syndrome

Loefgren syndrome

Loss of CAR T-cell persistence

Lupus anticoagulant hypoprothrombinaemia syndrome

Lymph gland infection

Lymph node abscess

Lymph node calcification

Lymph node fibrosis

Lymph node haemorrhage

Lymph node pain

Lymph node rupture

Lymph node tuberculosis

Lymph node ulcer

Lymph nodes scan abnormal

Lymph nodes scan normal

Lymphadenitis

Lymphadenitis bacterial

Lymphadenitis fungal

Lymphadenitis helminthic

Lymphadenitis viral

Lymphadenocyst

Lymphadenopathy

Lymphadenopathy mediastinal

Lymphangiectasia

Lymphangiectasia intestinal

Lymphangiectasia intestinal congenital

Lymphangioleiomyomatosis

Lymphangioma

Lymphangiopathy

Lymphangiosarcoma

Lymphangiosis carcinomatosa

Lymphangitis

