Monocyte percentage abnormal

Monocyte percentage decreased

Monocyte percentage decreased

Monocyte percentage increased Monocytic leukaemia in remission

Monocytopenia

Monocytopenia

Monocytosis

Mononuclear cell count

Mononuclear cell count abnormal

Mononuclear cell count decreased

Mononuclear cell count decreased

Mononuclear cell count increased

Mononuclear cell percentage

Mononucleosis syndrome

Multicentric reticulohistiocytosis

Myeloblast count

Myeloblast count decreased

Myeloblast count decreased

Myeloblast count increased

Myeloblast percentage

Myeloblast percentage decreased

Myeloblast percentage decreased

Myeloblast percentage increased

Myeloblast present

Myeloblastoma

Myelocyte count

Myelocyte count decreased

Myelocyte count decreased

Myelocyte count increased

Myelocyte percentage

Myelocyte percentage decreased

Myelocyte percentage decreased

Myelocyte percentage increased

Myelocyte present

Myelocytosis

Myelodysplastic syndrome

Myelodysplastic syndrome transformation

Myelodysplastic syndrome unclassifiable

Myelofibrosis

Myeloid leukaemia

Myeloid leukaemia in remission

Myeloid maturation arrest

Myeloid maturation arrest

Myeloid metaplasia

Myelolipoma

Myeloperoxidase deficiency

Myeloproliferative neoplasm

Myelosuppression

Natural killer T cell count

Natural killer T cell count decreased

Natural killer T cell count increased

Natural killer cell count

Natural killer cell count decreased

Natural killer cell count increased

Natural killer-cell leukaemia

Natural killer-cell lymphoblastic lymphoma

Necrotic lymphadenopathy

Neonatal alloimmune thrombocytopenia

Neonatal leukaemia

Neoplasm of thymus

Nephrogenic anaemia

Neuroacanthocytosis

Neutropenia

Neutropenia

Neutropenia neonatal

Neutropenia neonatal

Neutropenic colitis

Neutropenic infection

Neutropenic infection

Neutropenic sepsis

Neutropenic sepsis

Neutrophil Fc gamma RIIIb deficiency

Neutrophil Pelger-Huet anomaly present

Version: 1.0 Date: 01/06/2023

Neutrophil chemotaxis

Neutrophil chemotaxis abnormal

Neutrophil chemotaxis normal

Neutrophil count

Neutrophil count abnormal

Neutrophil count abnormal

Neutrophil count decreased

Neutrophil count decreased

Neutrophil count increased

Neutrophil count normal

Neutrophil function disorder

Neutrophil function test

Neutrophil function test abnormal

Neutrophil function test normal

Neutrophil hypersegmented morphology present

Neutrophil morphology

Neutrophil morphology abnormal

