Waldenstrom's macroglobulinaemia stage III Waldenstrom's macroglobulinaemia stage IV

Warm autoimmune haemolytic anaemia

White blood cell agglutination present

White blood cell analysis

White blood cell analysis abnormal

White blood cell analysis abnormal

White blood cell analysis normal

White blood cell count

White blood cell count abnormal

White blood cell count abnormal

White blood cell count decreased

White blood cell count decreased White blood cell count increased

White blood cell count normal

White blood cell disorder

White blood cell disorder

White blood cell morphology

White blood cell morphology abnormal

White blood cell morphology normal

White clot in blood present

Wiskott-Aldrich syndrome

X-linked lymphoproliferative syndrome

Acquired C1 inhibitor deficiency

Acute generalised exanthematous pustulosis

Acute respiratory failure

Administration related reaction

Administration site dermatitis

Administration site eczema

Administration site hypersensitivity

Administration site photosensitivity reaction

Version: 1.0 Date: 01/06/2023

Administration site rash

Administration site recall reaction

Administration site urticaria

Administration site vasculitis

HYPERSENSITIVITY

Airway remodelling

Allergic bronchitis

Allergic colitis

Allergic cough

Allergic cystitis

Allergic eosinophilia

Allergic gastroenteritis

Allergic hepatitis

Allergic keratitis

Allergic lymphangitis

Allergic oedema

Allergic otitis externa

Allergic otitis media

Allergic pharyngitis

Allergic reaction to excipient

Allergic respiratory disease

Allergic respiratory symptom

Allergic sinusitis

Allergic stomatitis

Allergic transfusion reaction

Allergy alert test positive

Allergy test positive

Allergy to chemicals

Allergy to fermented products

Allergy to immunoglobulin therapy

Allergy to surgical sutures

Allergy to vaccine

Alpha tumour necrosis factor increased

Alveolitis

Anal eczema

Anaphylactic reaction

Anaphylactic shock

Anaphylactic transfusion reaction

Anaphylactoid reaction

Anaphylactoid shock

Anaphylaxis treatment

Angioedema

Anti-insulin antibody increased

Anti-insulin antibody positive

Anti-insulin receptor antibody increased

Anti-insulin receptor antibody positive

Anti-neutrophil cytoplasmic antibody positive vasculitis

Antiallergic therapy

Antibody test abnormal

Antibody test positive

Antiendomysial antibody positive

Application site dermatitis

Application site eczema

Application site hypersensitivity

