CT 0.7.1	System Organ Class and Preferred Term (Safety Analysis Set)
CT-8.7.1	Incidence of TEAEs of at Least 2% in Any Brex Group and Greater Than Placebo
CT-8.7.2	by MedDRA System Organ Class and Preferred Term (Safety Analysis Set) Incidence of Drug-related TEAEs of at Least 2% in Any Brex Group and Greater
C1-6.7.2	Than Placebo by MedDRA System Organ Class and Preferred Term (Safety
	Analysis Set)
CT-8.8.1	Incidence of TEAEs by MedDRA System Organ Class, Preferred Term and Time to
0.0	First Onset (Safety Analysis Set)
CT-8.8.2	Incidence of Drug-related TEAEs by MedDRA System Organ Class, Preferred Term
	and Time to First Onset (Safety Analysis Set)
CT-8.9.1	Incidence of TEAEs for EPS (Safety Analysis Set)
CT-8.9.2	Incidence of TEAEs for Accidents and Injuries Including Fall (Safety Analysis Set)
CT-8.9.3	Incidence of TEAEs for Cerebrovascular Events (Safety Analysis Set)
CT-8.9.4	Incidence of TEAEs for Cardiovascular Events (Safety Analysis Set)
	· · · · · · · · · · · · · · · · · · ·

CT-8.9.5	Incidence of TEAEs for Effect on Glucose (Safety Analysis Set)
CT-8.9.6	Incidence of TEAEs for Effect on Lipids (Safety Analysis Set)
CT-8.9.7	Incidence of TEAEs for Effect on Weight (Safety Analysis Set)
CT-8.9.8	Incidence of TEAEs for Haematopoietic/Leukopenia (Safety Analysis Set)
CT-8.9.9	Incidence of TEAEs for Hypersensitivity (Safety Analysis Set)
CT-8.9.10	Incidence of TEAEs for Neuroleptic Malignant Syndrome (Safety Analysis Set)
CT-8.9.11	Incidence of TEAEs for Orthostatic Hypotension, Dizziness, and Syncope (Safety Analysis Set)
CT-8.9.12	Incidence of TEAEs for Effect on Prolactin (Safety Analysis Set)
CT-8.9.13	Incidence of TEAEs for QT Prolongation (Safety Analysis Set)
CT-8.9.14	Incidence of TEAEs for Rhabdomyolysis and CPK Elevation (Safety Analysis Set)
CT-8.9.15	Incidence of TEAEs for Seizures (Safety Analysis Set)
CT-8.9.16	Incidence of TEAEs for Somnolence (Safety Analysis Set)
CT-8.9.17	Incidence of TEAEs for Suicidality (Safety Analysis Set)
CT-8.9.18	Incidence of TEAEs for VTE (Thrombotic and Embolic Events) (Safety Analysis Set)
CT-8.9.19	Incidence of TEAEs for Pneumonia (Safety Analysis Set)
CT-8.10.1	Incidence of TEAEs by MedDRA System Organ Class and Preferred Term by Medical Care Category (Safety Analysis Set)
CT-8.10.2	Incidence of TEAEs by MedDRA System Organ Class and Preferred Term by Prior Antipsychotics (Safety Analysis Set)

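### The Haematopoietic/Leukopenia adverse-event category pools white-cell falls, rises and normal results, so its total cannot be read as a leukopenia rate (minor)

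*SAP*

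**What the plan says.** Appendix 4 of the SAP gives the preferred terms for each adverse event of interest. One block is labelled "HAEMATOPOIETIC/LEUKOPENIA". SAP 9.2.1 lists the same category under the name "Blood disorder-related AEs" and plans numbers and proportions of subjects, broken down by system organ class and preferred term, for each treatment group and for brexpiprazole overall. Appendix 5 has one summary table for it, CT-8.9.8, whose title begins "Incidence of TEAEs for Haematopoietic/Leukopenia (Safety Analysis Set", and one listing, CT-9.4.8.

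Within that one block stand:

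- terms for a fall, such as *Leukopenia*, *Neutropenia* and "White blood cell count decreased";
- terms for a rise, such as "Leukocytosis", "Neutrophil count increased" and "White blood cell count increased";
- terms for a normal result, such as "White blood cell count normal";
- anaemia, coagulation, leukaemia and lymphoma, spleen, malaria and blood-group terms.

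Roughly 60 terms are printed twice. Neither SAP 9.2.1 nor Appendix 5 plans a subtotal for leukopenia, neutropenia or any white-cell decrease.

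**The concern.** Leukopenia is named in the category label and in the table title, so a reader of CT-8.9.8 will look there for the leukopenia result. Nothing planned gives it at subject level. A subject with neutropenia and a subject with a raised white count contribute identically to the category total.

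The individual preferred-term rows do not fill the gap. One subject can have several of these terms, so the rows cannot be added to give the number of subjects with any white-cell fall. Where events are few and spread over dozens of terms, a grouped count is the main reason to have a category of interest at all.

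What is at stake is how one descriptive safety table is read. The total could be quoted as a leukopenia rate when it is not one, and a difference between arms in falls would look smaller in relative terms than it is.

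**Working it through.** The plan states no figure on this point, so there is none to reproduce. The check has two parts.

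**1. Where falls and rises are kept apart, and where they are pooled**

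| Place | Falls separable from rises? |
|---|---|
| CT-8.9.8, category total | No; it also pools normal results and unrelated blood terms |
| CT-8.9.8, preferred-term rows | Yes, term by term, but not as a count of distinct subjects |
| CT-9.4.8 and AE-1 listings | Yes, by counting subjects by hand |
| SAP 9.3 shift tables | Yes: low, within range and high are separate |
| SAP Appendix 2, absolute neutrophil count (1,000/mm³ or less) and neutrophils (15% or less) | Yes, low only |
| SAP Appendix 2, white blood count (2,800/mm³ or less, or 16,000/mm³ or more) | No, both directions in one row |

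SAP 9.2.1 shows no table shell. That CT-8.9.8 carries a category total is inferred from its plan to give numbers and proportions of subjects with each event of interest.

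**2. How far pooling moves the contrast between arms**

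Inputs from the documents are the planned sizes (SAP section 4): 148 on 2 mg, 111 on 1 mg and 148 on placebo, so brexpiprazole overall is 148 + 111 = 259. The documents give no event rates. The following are assumptions for illustration: white-cell falls in 3% on brexpiprazole and 1% on placebo, and no subject with both a fall and another listed term.

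Falls alone: 259 × 0.03 = 7.8 subjects against 148 × 0.01 = 1.5; ratio 3.0, difference 2.0 points.

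Let other listed terms occur at the same rate q in both arms. The ratio for the total is (0.03 + q)/(0.01 + q), and the difference is (0.03 + q) − (0.01 + q) = 0.02.

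| q | Total, brexpiprazole v placebo | Ratio | Difference |
|---|---|---|---|
| 0% | 3% v 1% | 3.0 | 2.0 points |
| 1% | 4% v 2% | 2.0 | 2.0 points |
| 2% | 5% v 3% | 1.67 | 2.0 points |
| 5% | 8% v 6% | 1.33 | 2.0 points |
| 10% | 13% v 11% | 1.18 | 2.0 points |

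If the other terms differ between arms, the total can move either way:

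- 1% on brexpiprazole and 3% on placebo: 0.03 + 0.01 = 4% against 0.01 + 0.03 = 4%, so the contrast vanishes.
- 3% on brexpiprazole and 1% on placebo: 0.03 + 0.03 = 6% against 0.01 + 0.01 = 2%, a difference of 4 points, double that for falls alone.

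In every case the preferred-term rows for falls are unchanged.

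**The case against.** The strongest reply is that the category is openly broad. SAP 9.2.1 calls it blood-disorder related, and the title puts haematopoietic before leukopenia, so a wide search is consistent with the name. No test is planned on this table. Protocol 5.2 asks for one unifying diagnosis where possible, and 5.1 makes a laboratory value an adverse event only if it is medically relevant, leads to discontinuation or meets the criteria for seriousness. An infection with a raised white count should therefore mostly be reported as the infection, which limits how many rises reach the list. All of this stands, and it is why the point is minor. It does not supply the missing subject-level count of decreases.

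Four stronger readings are tempting, and the documents do not support them:

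- *The table hides leukopenia.* It does not. Reporting is by preferred term, and the shift tables and the absolute neutrophil count criterion show falls separately.
- *Rises cancel falls.* Within an arm, subject counts only add. A zero contrast between arms needs the other terms to be more frequent on placebo. Protocol 2.1 names pneumonia and other infections among the causes of death associated with atypical antipsychotics. If rises track infection, that concern points towards more rises on brexpiprazole, which would inflate the total.
- *The count cannot be recovered.* It cannot be had from the preferred-term rows, but it can be had from CT-9.4.8 or AE-1. It is simply not planned.
- *The terms printed twice are a ready-made leukopenia set.* The pattern suggests that two searches were merged, but the SAP does not say so, and terms repeat in other categories too (*Extrapyramidal disorder*, for example). The repeated terms include direction-neutral ones (*Full blood count abnormal*, *White blood cell disorder*), while *Pancytopenia*, *Autoimmune neutropenia* and *Myelosuppression* are printed once.

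**Conclusion.** The point holds as a minor reporting defect. The total for this category mixes decreases, increases, normal results and unrelated blood disorders. It cannot be read as a leukopenia rate, and its relative contrast between arms is diluted. Under the assumed 3% v 1% for falls, the ratio drops from 3.0 to between 2.0 and 1.18 as the equal background rises from 1% to 10%, with the absolute difference unchanged. A full offset is a special case that needs unequal backgrounds. These sizes rest on assumed rates, on planned rather than actual numbers, and on no overlap between subjects. The mixing of directions and the absence of a planned subtotal rest on the text alone. The primary analysis and its error rate are not affected.

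**What to change.** Keep the broad category and its rows by system organ class and preferred term. Then:

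1. Add to CT-8.9.8 a prespecified row for subjects with at least one white-cell-decrease term, each subject counted once, and flag those subjects in CT-9.4.8.
2. Define that set in Appendix 4 by the direction of the term, not by which terms are printed twice. It should include, for example, *Pancytopenia*, *Autoimmune neutropenia* and *Myelosuppression*. State where direction-neutral terms (those ending in abnormal or disorder) are placed.
3. Show increase terms as a separate row.
4. Remove duplicate entries and the normal-result terms.

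The cost is an edit to Appendix 4 and one or two more rows in a descriptive table. The set needs a short medical review, because it cannot be taken over unchanged from the repeated terms. No other analysis changes.
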